2.2. Inclusion and Exclusion Criteria for Case Selection

Inclusion Criteria:

- Patients undergoing lumbar disc herniation surgery at Dokuz Eylül University Hospital.
- Patients who have read and consented to the informed consent form for the study.
- Age 18 years or older.
- Surgery duration exceeding 2 hours.

Exclusion Criteria:

- Patients unwilling to participate in the study.
- Surgery duration less than 2 hours.
- Patients under the age of 18.
- Patients with a history of abdominal surgery.
- Patients who received antibiotic therapy for intestinal pathology within the last 3 weeks.
- Patients with known abdominal pathologies that are suspected to alter the microbial flora (e.g., Crohn's disease, ulcerative colitis, celiac disease).

Patient records, clinical histories, examination findings, and relevant laboratory results were electronically recorded. All these data were documented on a prepared data collection form and transferred to an electronic database.

2.3. Studying samples collected from patients

Sample analyses were performed using an Ultivo tandem mass spectrometer (6465B, Agilent Technologies, Santa Clara, CA, USA) connected to an Agilent HPLC system. The analyses of kynurenine pathway metabolites were conducted using the CE-IVD certified and validated commercial Jasem Kynurenine Pathway Metabolites LC-MS/MS analysis kit (Sem Laboratory Devices Marketing Co., Istanbul, Turkey). The analytical process was completed using the mobile phases (mobile phase A and B), analytical column, calibrators, stable isotope-labeled internal standard (IS) mixture, and sample preparation reagents provided with the commercial kit.

2.4. Sample Preparation for Kynurenine Pathway Metabolite Analysis

Preparation of the calibrator set; 100 µl calibrator was taken into the HPLC vial, 50 µl internal standard was added and diluted with 250 µl Reagent-1 and injected into the LC-MS/MS system. Sample Preparation; 100 µl serum/plasma/control sample was taken into Eppendorf, and 50 µl internal standard was added and vortexed for 5 seconds after protein precipitation with 250 µl reagent-1. It was centrifuged at 4500rpm for 5 minutes. The resulting upper phase was taken into the HPLC vial and transferred to the LC-MS/MS system.

2.5. Ethichs

Ethics committee approval for this study was received locally from the University Izmir Dokuz Eylul University Hospital (decision dated 31.08.2022, numbered 7131-GO). The study was conducted following the principles of the Declaration of Helsinki. Since our study was planned retrospectively, approval was obtained from the ethics committee without obtaining informed consent from the patients.

References

- [1] R. Guo, L. H. Chen, C. Xing, and T. Liu, “Pain regulation by gut microbiota: molecular mechanisms and therapeutic potential,” *Br J Anaesth*, vol. 123, no. 5, pp. 637–654, Nov. 2019, doi: 10.1016/J.BJA.2019.07.026.
- [2] E. A. Mayer, R. Knight, S. K. Mazmanian, J. F. Cryan, and K. Tillisch, “Gut microbes and the brain: paradigm shift in neuroscience,” *J Neurosci*, vol. 34, no. 46, pp. 15490–15496, Nov. 2014, doi: 10.1523/JNEUROSCI.3299-14.2014.
- [3] S. H. Rhee, C. Pothoulakis, and E. A. Mayer, “Principles and clinical implications of the brain-gut-enteric microbiota axis,” *Nat Rev Gastroenterol Hepatol*, vol. 6, no. 5, pp. 306–314, 2009, doi: 10.1038/NRGASTRO.2009.35.
- [4] A. I. Basbaum, D. M. Bautista, G. Scherrer, and D. Julius, “Cellular and Molecular Mechanisms of Pain,” *Cell*, vol. 139, no. 2, p. 267, Oct. 2009, doi: 10.1016/J.CELL.2009.09.028.
- [5] J. F. Cryan and T. G. Dinan, “Mind-altering microorganisms: the impact of the gut microbiota on brain and behaviour,” *Nat Rev Neurosci*, vol. 13, no. 10, pp. 701–712, Oct. 2012, doi: 10.1038/NRN3346.
- [6] I. K. Hwang *et al.*, “Changes in the expression of mitochondrial peroxiredoxin and thioredoxin in neurons and glia and their protective effects in experimental cerebral ischemic damage,” *Free Radic Biol Med*, vol. 48, no. 9, pp. 1242–1251, May 2010, doi: 10.1016/J.FREERADBIOMED.2010.02.007.
- [7] T. R. Sampson and S. K. Mazmanian, “Control of brain development, function, and behavior by the microbiome,” *Cell Host Microbe*, vol. 17, no. 5, pp. 565–576, May 2015, doi: 10.1016/J.CHOM.2015.04.011.
- [8] P. Bercik *et al.*, “The intestinal microbiota affect central levels of brain-derived neurotropic factor and behavior in mice,” *Gastroenterology*, vol. 141, no. 2, 2011, doi: 10.1053/J.GASTRO.2011.04.052.
- [9] A. Agus, J. Planchais, and H. Sokol, “Gut Microbiota Regulation of Tryptophan Metabolism in Health and Disease,” *Cell Host Microbe*, vol. 23, no. 6, pp. 716–724, Jun. 2018, doi: 10.1016/J.CHOM.2018.05.003.

## Statistical Analysis Plan (SAP)

The Shapiro-Wilk goodness-of-fit test was used to determine whether the distributions of numerical variables conformed to a normal distribution. For numerical variables that followed a normal distribution, descriptive statistics such as mean and standard deviation were provided. For numerical variables that did not follow a normal distribution, descriptive statistics such as median and interquartile range were given. Percentages and frequency tables were provided for categorical variables. To compare the patient and control groups, variables that met the normality assumption were analyzed using the parametric test for the significance of the difference between two means, while those that did not meet the normality assumption were analyzed using the non-parametric Mann-Whitney U test. The assumption of homogeneity of variances was examined with the Levene test statistic. Kruskal-Wallis analysis of variance was used to examine whether there were differences between diagnosis groups in terms of age. The relationship between age and numerical parameters was examined with the Spearman rank correlation coefficient since the age variable did not meet the normality assumption. Whether there were differences in numerical measurements between diagnostic groups was examined with one-way analysis of variance, and when the parametric assumptions of one-way analysis of variance were not met, it was examined with the Kruskal Wallis test. The differences between the groups were examined using the Bonferroni test approach, one of the Post-Hoc tests.

The area under the ROC curve was used to evaluate the performance of the diagnostic test. The Youden index (J), which assumes sensitivity and selectivity, or false positive and false negative rates, as equally important, was used to determine the best cutoff point.

Statistical significance level was accepted as  $p < 0.05$ . Categorical variables are presented as percentages and numbers, and continuous variables are presented as mean (mean), standard deviation (SD) or median, 25th Quarter (Q1) and 75th Quarter (Q3). The suitability of the variables to normal distribution was examined using visual (histogram and probability graphs) and analytical methods (Kolmogorov Smirnov Test). In comparing two independent groups, Mann Whitney U Test was used for those that did not show normal distribution. Spearman correlation analysis was performed to

evaluate the relationships of continuous variables. In comparing three or more measurements of dependent groups, ANOVA test was used for repeated measurements for data that conformed to normal distribution, and the Friedman test was used for data that did not comply with normal distribution. Wilcoxon test was used for pairwise group comparisons in repeated measurements that were statistically significant. The results were evaluated at a 95% confidence interval, with alpha error set at 0.05. Statistical evaluation was made using the Statistical Package for Social Sciences (SPSS) for Windows 26.0 (IBM SPSS Inc., Chicago, IL) program.

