An important feature of the microbiota is that the signaling molecules it produces through Tryptophan metabolism can affect pain mechanisms. Some bacteria, especially members of the microbiota such as Escherichia Coli, can produce tryptophan.[9] Furthermore, commensal bacterial species that produce AhR ligands play an important role in regulating AhR activity. [10], [11]. The ability of these bacteria to metabolize Tryptophan can lead to the production of the neurotransmitter tryptamine. [12].

Pain is a subjective experience that cannot be directly observed or measured by biological tests. Therefore, the assessment of pain is largely based on the individual's own subjective interpretation. Although its adequacy in pain assessment is questioned, the method used is generally Visual Analogue Scale (VAS).

In this study, we aimed to examine the effect of microbiota and tryptophan metabolites on pain perception in patients undergoing lumbar disc herniation surgery. We evaluated how the gut microbiota affects pain mechanisms by measuring levels of tryptophan metabolites and assessing pain severity in the pre- and postoperative periods.

2. Materials and Methods

In this study, we adhered to the STROBE (Strengthening the Reporting of Observational Studies in Epidemiology) guidelines to ensure the quality and transparency of the reporting of our observational study.

Our study includes 37 lumbar disc herniation (LDH) surgeries performed in Dokuz Eylül University Faculty of Medicine Central Operating Rooms Brain and Nerve Surgery Hall. For the blood samples in which we evaluated tryptophan metabolites; 2 mL of blood was used from the blood samples taken during routine surgery preparation for the patients and from the routine blood samples taken in the postoperative period, and no additional invasive intervention was performed. We elucidated the relationship between tryptophan metabolites (Picolinic Acid, 3-Hydroxykynurenone, Anthranilic Acid, Kynurenone, Quinolinic Acid, Kynurenic Acid, Xanthurenic Acid) and their variations due to microbiota alterations with VAS in acute pain. Preoperative, postoperative, 8th-hour, and 24th-hour blood samples were routinely collected from patients, with 2 ml of sample material used each time. Concurrently, pain information and vital signs were recorded. After the necessary centrifugation processes, the tryptophan metabolites were analyzed by the relevant laboratory team.

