### **Evaluation of Sample Size Calculation for Correlation Analysis between VAS and Tryptophan Metabolite Measurements**

The sample size calculation for assessing the correlation between VAS (Visual Analog Scale) and tryptophan metabolite measurements was conducted using G\*Power software, employing a Point biserial model test. It was determined that a minimum sample size of 26 participants is required to achieve a statistical power of 80% with a significance level (alpha) of 5% and an effect size of 0.50 (1).

This approach ensures that the study is adequately powered to detect meaningful correlations between pain perception (measured by VAS) and the levels of tryptophan metabolites in the blood, contributing to the robustness of the statistical analysis.

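### The Youden cutoff is chosen from the study data with no validation or optimism correction, so J and any sensitivity and specificity quoted at that cutoff will be biased upward; the AUC is not affected.

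*SAP*

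**What the plan says.** The SAP's main section gives two sentences to ROC analysis. The first sets the performance measure: "The area under the ROC curve was used to evaluate the performance of the diagnostic test". The second says that the Youden index, which weights the two error rates equally, "was used to determine the best cutoff point". The test, the condition it is meant to detect and the groups being separated are not named.

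Neither document gives a cutoff fixed in advance, a hold-out or external sample, cross-validation, or a bootstrap correction. On the data available, Protocol section 2 says: "Our study includes 37 lumbar disc herniation (LDH) surgeries". No second cohort is described. The SAP mentions a control group, but gives it no size, and the protocol has no counterpart.

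The only sample-size statement in the SAP is for the correlation between VAS and metabolites: "a minimum sample size of 26 participants is required", for "an effect size of 0.50", "employing a Point biserial model test". Nothing is said about the precision of the ROC analysis or of a cutoff.

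**The concern.** The Youden cutoff is the threshold at which sensitivity + specificity − 1 is largest in the observed data. If sensitivity and specificity are then read at that threshold from the same patients, they are the most favourable of many candidates and include the chance variation that made that threshold win. In a sample of this size that component is not small. Even a marker unrelated to the condition gives a J above zero on average, and a weak marker looks clearly better than it is.

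At stake is how a reported cutoff would be read. Readers usually take a cutoff and its sensitivity and specificity as what to expect in new patients, and the plan has nothing that would correct or qualify that reading.

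**Working it through.** **Step 1. The plan's own figure.** Inputs from the SAP sample-size section: r = 0.50, alpha 0.05, power 80%, point biserial model. With df = N − 2 and noncentrality δ = √(N r²/(1 − r²)), N = 26 gives δ = √(26 × 0.25/0.75) = 2.94 on 24 df. Two-sided power is 0.806; N = 25 gives 0.789. The stated 26 is therefore reproduced, on the assumption of a two-sided test (sidedness is not stated). This figure is for a correlation and does not bear on the cutoff.

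**Step 2. Model for the cutoff.** Inputs: 37 patients (Protocol section 2) and a cutoff that maximises J (SAP). Assumptions, because the SAP gives no ROC groups: a continuous marker, normal with equal variance in both states, and either the 37 patients split in two or 37 observations against 37 others.

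- Separation of the states: μ = √2 · Φ⁻¹(AUC). For AUC 0.7, μ = 1.414 × 0.524 = 0.742.
- Apparent J: the maximum over cutoffs c of observed sensitivity(c) + specificity(c) − 1.
- True J at the selected cutoff c*: Φ(μ − c*) − Φ(−c*).
- Optimism: mean apparent J minus mean true J at c*.
- Best J attainable with the true distributions known: 2Φ(μ/2) − 1. For AUC 0.7 this is 2 × 0.645 − 1 = 0.29.

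The unpaired settings were simulated with 40,000 datasets each.

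**Step 3. Marker with no information (true AUC 0.5, true J = 0).**

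| Groups | Mean apparent J, direction fixed | Mean apparent J, direction from data |
|---|---|---|
| 18 / 19 | 0.18 | 0.26 |
| 15 / 22 | 0.19 | 0.27 |
| 11 / 26 | 0.20 | 0.29 |
| 9 / 28 | 0.21 | 0.31 |
| 5 / 32 | 0.26 | 0.38 |
| 37 / 37 independent | 0.13 | 0.19 |
| 37 / 37 paired, within-patient correlation 0.5–0.8 | 0.12–0.13 | 0.15–0.17 |

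The paired row would apply if, for example, preoperative samples were compared with postoperative samples from the same patients.

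**Step 4. Informative marker, direction fixed.**

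| True AUC | Groups | Apparent J | True J at cutoff | Optimism |
|---|---|---|---|---|
| 0.6 | 18 / 19 | 0.293 | 0.117 | 0.175 |
| 0.6 | 9 / 28 | 0.321 | 0.115 | 0.206 |
| 0.6 | 37 / 37 | 0.245 | 0.120 | 0.125 |
| 0.7 | 18 / 19 | 0.416 | 0.257 | 0.159 |
| 0.7 | 9 / 28 | 0.441 | 0.252 | 0.190 |
| 0.7 | 37 / 37 | 0.375 | 0.264 | 0.111 |
| 0.8 | 18 / 19 | 0.555 | 0.415 | 0.140 |
| 0.8 | 9 / 28 | 0.579 | 0.407 | 0.172 |
| 0.8 | 37 / 37 | 0.520 | 0.424 | 0.097 |

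The 37 / 37 rows are for independent groups. At AUC 0.6 the overstatement exceeds the true J in all three settings.

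**Step 5. What a bootstrap correction achieves.** For the 18/19 split, with the cutoff re-selected in each of 100 resamples, mean J moved from 0.19 to 0.08 (truth 0) at AUC 0.5. At AUC 0.7 it moved from 0.41 to 0.31 (truth 0.25). The share of the bias removed is (0.19 − 0.08)/0.19 = 58% and (0.41 − 0.31)/(0.41 − 0.25) = 63%: more than half, but not all.

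**The case against.** **The SAP's performance measure is the AUC.** This stands. For a single marker with its direction set beforehand, the AUC is not affected by where the cutoff falls. A reader might infer that the whole ROC assessment is inflated; the documents do not support that. The bias is confined to J, sensitivity and specificity at the chosen cutoff.

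**Same-sample reporting is inferred.** The SAP does not say that sensitivity and specificity at the cutoff will be reported, or from which data. With one cohort and no validation step the same-sample reading is the natural one, and a cutoff is of little use without those two figures. The point is still conditional on their being reported.

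**The size depends on a design that is not stated.** This also stands. It is tempting to say flatly that a useless marker would show J of 0.2–0.3, or that the maximum is taken over at most 36 thresholds. Both presume 37 single observations split in two. The SAP's mention of controls, or the repeated blood samples in Protocol section 2.1, could lead to 37 against 37, with up to 73 thresholds between 74 distinct values and a null J of 0.12–0.19.

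**The SAP does not say that the test is a metabolite.** Correct. The protocol lists seven metabolites, and the best of seven independent null markers would average a J of about 0.34–0.42 (18/19 or 12/25 split). The SAP states no such selection, so that figure is not part of this point.

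**The harm is limited.** A J of 0.2 is, for instance, 60% sensitivity with 60% specificity, which impresses few readers beside an AUC near 0.5. The protocol does not mention ROC analysis, neither document proposes clinical use of a cutoff, and the sample-size calculation concerns the correlation. This limits the weight of the point but does not remove the bias.

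**Conclusion.** The concern holds in a limited form. Followed as written, the SAP yields a data-chosen cutoff, and J and any sensitivity and specificity quoted at it will be too favourable on average.

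- **No information:** mean apparent J is about 0.18–0.21 with direction fixed, or 0.26–0.31 with direction taken from the data, for splits of the 37 patients from 1:1 to about 1:3. It is about 0.12–0.13 or 0.15–0.19 for 37 against 37, independent or paired.
- **True AUC 0.6–0.8:** the overstatement is about 0.14–0.21 for the split cohort and about 0.10–0.12 for independent 37 against 37.

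These are averages under a normal, equal-variance marker and assumed group sizes. The direction of the bias does not depend on the group sizes, but its magnitude does. The missing definition of the ROC groups is a separate and prior defect; settling it would fix the size of this bias without removing it. The point should be corrected, but it does not touch the correlation analysis on which the sample size rests.

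**What to change.** First name the marker, the reference state and the groups for the ROC; the correction cannot be run without them. Then replace the cutoff sentence with wording to this effect:

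> The AUC with its 95% confidence interval is the main discrimination result. The Youden cutoff is exploratory. J, sensitivity and specificity at the cutoff are reported after bootstrap optimism correction, with the cutoff re-selected in every resample (patients are resampled if measurements are paired), with 95% confidence intervals and an interval for the cutoff itself. The correction reduces but does not fully remove the optimism, so the cutoff requires validation in other data.

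State also whether the direction of the marker is set in advance, since reading it from the data adds to the bias.

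The cost is a short bootstrap script on data already collected, with no further patients, and reported figures that will look less favourable. If the ROC paragraph has no application in this study, delete it instead; the point then falls away.

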2.1. Data Collection

Blood samples were planned and collected from patients during the preoperative evaluation, at the 8th postoperative hour, and at the 24th postoperative hour, adhering to clinical routines for these procedures. Concurrently with each blood draw, the patient's VAS score, the nature of the pain, and vital signs were recorded. At the end of the surgery, procedures were performed in the recovery unit according to the protocols, and the same data along with vital signs were recorded. Blood samples collected from the patients were centrifuged at 4000 rpm for 10 minutes, after which the serum and plasma portions were transferred to Eppendorf tubes. The blood samples were stored at -80°C for preservation. For the same patients, 24-hour postoperative blood collection was performed, and similar data, including VAS scores, were recorded.

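### The metabolite-VAS conclusion rests on an unadjusted Spearman correlation; it should be age-adjusted, with analgesia handled as a sensitivity analysis and the conclusion worded as an association

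*SAP*

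**What the plan says.** Item 6 of the Protocol's Study Follow-Up Table sets the objective: the correlation of seven metabolites with VAS. The last paragraph of the Introduction goes further and words the aim as an effect of microbiota and metabolites on pain perception.

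The only SAP method that fits the objective is in the general methods text: "Spearman correlation analysis was performed to" "evaluate the relationships of continuous variables". No adjustment is named there or in the sample size section.

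Age appears in the SAP twice, each time in a separate analysis: "The relationship between age and numerical parameters was examined with the Spearman rank correlation coefficient since the age variable did not meet the normality assumption", and "Kruskal-Wallis analysis of variance was used to examine whether there were differences between diagnosis groups in terms of age". Age is therefore collected. Eligibility is "Age 18 years or older" with no upper limit (Protocol 2.2), so restriction does not control it.

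Protocol 2.1 lists VAS, the nature of the pain and vital signs as the items taken with each draw. After surgery, "procedures were performed in the recovery unit according to the protocols"; those protocols are not described. Neither document mentions analgesia. Protocol 2.2 adds that "Patient records, clinical histories, examination findings, and relevant laboratory results were electronically recorded", and that a data collection form was used. The form is not shown.

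**The concern.** A bivariate correlation answers whether VAS and a metabolite move together across patients. It does not separate a link between the two from the influence of something that drives both. Age is an obvious candidate because the sample can span all adult ages. The SAP looks at age on its own, which might reveal such a link but does not remove it from the metabolite-VAS estimate.

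Postoperative ratings raise a second problem. A VAS given after recovery and ward care reflects that care as well as the patient's perception of pain. Without a record of analgesia, a reader cannot tell how much.

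Both matter because of the aim. With 37 patients, an omitted common cause of moderate strength could produce a significant correlation where there is no link, or hide a link of the size the study was planned to find. In either case the result would not support a statement about an effect on pain perception.

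**Working it through.** **Inputs from the documents.** n = 37 (Protocol 2); alpha 0.05, power 80%, effect size 0.50 and minimum sample size 26, point biserial model (SAP, sample size section). The documents give no correlation of age or analgesia with VAS or with any metabolite, so those values are assumed and shown as a range.

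**1. The plan's own figure.** Noncentral t with df = N − 2 and noncentrality √(N·ρ²/(1 − ρ²)). For N = 26 and ρ = 0.50 the noncentrality is √(26 × 0.25/0.75) = 2.94. Two-sided power is 0.806, so 26 reproduces. The sample size is not the defect; the model simply has no covariates.

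**2. Inflation by a common cause.** Let a third variable correlate a with VAS and b with a metabolite, with no link once it is held fixed. The raw correlation is then r = a·b. The chance of p < 0.05 is approximately Φ(m − 1.96) + Φ(−m − 1.96), with m = atanh(r)·√((37 − 3)/1.06). For a = b = 0.5, r = 0.25, m = 0.2554 × 5.66 = 1.45, and the rate is 0.304. Simulated rates at n = 37 (5,000 datasets per setting):

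| a / b | raw r | unadjusted Spearman |
|---|---|---|
| 0.3 / 0.2 | 0.06 | 0.062 |
| 0.4 / 0.3 | 0.12 | 0.101 |
| 0.4 / 0.4 | 0.16 | 0.147 |
| 0.5 / 0.4 | 0.20 | 0.208 |
| 0.5 / 0.5 | 0.25 | 0.301 |

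Partial Spearman, adjusting for the third variable, gives 0.044 to 0.058 across these settings.

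**3. Masking.** With a true partial correlation of 0.50, raw r = 0.50·√((1 − a²)(1 − b²)) + a·b. For a = 0.3, b = −0.3: 0.50 × 0.91 − 0.09 = 0.365. For a = 0.5, b = −0.5: 0.50 × 0.75 − 0.25 = 0.125. In simulation (10,000 datasets per setting) the power of the unadjusted test falls from 86% without a third variable to 56% and 11%. The partial test keeps 83% and 81%.

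**4. Cost of adjusting for age.** The correlation detectable with 80% power is tanh(2.80/√(n − 3 − q)) for q covariates. With q = 0: tanh(2.80/√34) = 0.447. With q = 1: tanh(2.80/√33) = 0.452. Power at ρ = 0.50 with the Spearman variance factor 1.06 goes from 87.5% to 86.5%.

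**5. Analgesia as a response to pain.** Steps 2 and 3 assume a common cause. Suppose instead that the metabolite acts on pain, analgesia follows pain, and VAS is pain minus an analgesic effect plus noise (n = 37; 4,000 datasets per setting; all parameters assumed). With no metabolite-pain link, the unadjusted test rejects 4.5% to 5.4% of the time, so there is no inflation. With a true link of 0.50:

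| correlation of analgesia with pain | analgesic weight | power unadjusted | power adjusted for analgesia |
|---|---|---|---|
| 0.5 | 0.2 | 73% | 61% |
| 0.7 | 0.2 | 72% | 44% |
| 0.3 | 0.4 | 67% | 71% |

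In the middle row the mean correlation also falls, from 0.40 to 0.30, so adjustment biases the estimate towards zero.

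**The case against.** The strongest reply has four parts.

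- **The stated objective is a correlation.** An unadjusted Spearman coefficient answers item 6 of the Follow-Up Table as written. This stands. The difficulty arises with the Introduction's effect wording.
- **Analgesia may be a consequence of pain.** This also stands, and it changes the remedy. A reader might infer that the conclusion should rest on an analgesia-adjusted correlation, or that 6% to 30% is the harm to expect from ignoring analgesia. Neither follows. The documents give no route from analgesia to metabolites. Step 5 shows no false-positive inflation in the response structure, and shows that adjustment can do damage.
- **Age is not ignored.** A reader might infer that the SAP regards age as related to the metabolites and VAS and then omits it. The text says only that the relationship was examined. It stands beside group comparisons and an ROC analysis that do not match the single surgical cohort in the Protocol, so it says little about how this study views age. The case for adjustment rests on the open age range and on age being available, not on that sentence.
- **Analgesic data may already be held.** A reader might infer that analgesia was never recorded. The documents show only that it is not among the items listed at each draw; the unseen data form may contain it.

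The documents contain no results, so nothing here shows that a reported association is wrong.

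**Conclusion.** The concern holds in a limited form. The only planned metabolite-VAS analysis is unadjusted, age is available but unused in it, and analgesia is not listed as recorded with the ratings. If a third variable is linked to both VAS and a metabolite, the raw correlation can mislead in either direction. At n = 37 the false-positive rate is about 6% to 30% per test for assumed covariate correlations of 0.2 to 0.5, and power at a true partial correlation of 0.50 can fall from 86% to between 56% and 11% for opposing correlations of 0.3 to 0.5. At the weak end the inflation is negligible. These are scenarios for a common cause such as age might be; the documents allow no estimate of the actual size or direction. For analgesia the structure itself is uncertain, which supports recording it and testing sensitivity, but not making the adjusted value the main result.

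**What to change.** Three changes to the SAP and the reporting:

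1. Base the metabolite-VAS conclusion on a partial Spearman correlation (or a rank regression) adjusted for age, and print the unadjusted value beside it. Age is already collected. The cost is one degree of freedom: the detectable correlation moves from about 0.447 to 0.452.
2. Extract analgesic exposure before each VAS rating from existing records, and pre-specify an analgesia-adjusted correlation as a sensitivity analysis only. State how different drugs are reduced to one exposure variable, and say that the adjusted value may be biased or less powerful if analgesia responds to pain. The cost is chart extraction for 37 patients and a few lines of text. If the records cannot be retrieved, report that as a limitation.
3. Word the conclusion as an association with VAS under treatment, not as an effect on pain perception. This costs nothing and is needed whatever the sensitivity analysis shows, since age adjustment does not remove other shared causes.

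### No multiplicity adjustment is stated for the pairwise Wilcoxon tests between time points; with four times the error rate per variable can reach about 12% rather than 5%

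*SAP*

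**What the plan says.** **Overall test.** The SAP, under its single heading Statistical Analysis Plan, says: "In comparing three or more measurements of dependent groups, ANOVA test was used for repeated measurements" where the data are normal; otherwise "the Friedman test was used for data that did not comply with normal distribution".

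**Follow-up.** "Wilcoxon test was used for pairwise group comparisons in repeated measurements that were statistically significant". The next sentence reads "The results were evaluated at a 95% confidence interval, with alpha error set at 0.05". No correction is attached to either sentence, and the general threshold given earlier is p < 0.05.

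**The only adjustment named.** "The differences between the groups were examined using the Bonferroni test approach, one of the Post-Hoc tests". This comes directly after the one-way ANOVA or Kruskal-Wallis comparison of diagnostic groups, which are independent groups. The Protocol describes one cohort of 37 operations and defines no diagnostic groups.

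**Number of time points.** Protocol section 2 says "Preoperative, postoperative, 8th-hour, and 24th-hour blood samples were routinely collected from patients", with pain recorded at the same times. Section 2.1 lists three blood draws (preoperative, 8 hours, 24 hours), with VAS at each. It adds that the same data were recorded in the recovery unit, without mentioning a blood draw there.

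**The concern.** The within-patient comparisons over time are the group-type comparisons that this design supports, and they are the ones with no stated correction. The plan relies on the overall test as a gate. A gate protects the pairwise tests when all times are equal, because then it opens in only about 5% of datasets. Surgery may well shift at least one time. The gate then opens almost every time, and every pair that is truly equal is tested at 0.05.

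At stake are statements about when pain or a metabolite changes (for example, between 8 and 24 hours). Such statements could be false more often than the stated alpha implies. A reader of the results also could not tell whether the reported p-values were adjusted.

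**Working it through.** **The plan's own figures.** The SAP gives no family-wise error rate for these comparisons, only alpha 0.05. Its one calculated figure is the minimum of 26 patients for the correlation. That reproduces: an exact two-sided point biserial calculation with r = 0.50 and alpha 0.05 gives power 0.806 at n = 26 and 0.789 at n = 25. It does not bear on this point.

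**Inputs.** Alpha 0.05 (SAP; sidedness is not stated, two-sided assumed). Patients: 37 (Protocol section 2); 26 (SAP minimum) was also run. Times: four (Protocol section 2) or three blood draws (section 2.1). Pairs = k(k − 1)/2, so 6 for k = 4 and 3 for k = 3. The sizes of the shifts are assumptions; the documents give none.

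**Three times, reasoned.** If all three are equal, the gate limits the error to about 5%. If one differs, only one true-null pair remains, tested at 0.05. Either way the error is at most about 5%.

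**Four times, reasoned.**
- All equal: the gate limits the error to about 5%.
- One clearly different, three equal: the gate is open and three true-null pairs remain. In large samples the error is P(range of three equal means > 1.96 × √2 = 2.772) on the studentized range distribution, which is 12.2%.
- Two separate equal pairs: 1 − (1 − 0.05)² = 9.75%.
- Only one equal pair left: at most 5%.

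**Simulation.** 40,000 datasets per setting, normal data with a patient effect, overall test at 0.05, then Wilcoxon signed-rank at 0.05 on the true-null pairs. Ranges cover n = 26 and n = 37.

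| True pattern | Friedman gate | ANOVA gate | Friedman gate, then Bonferroni over all pairs |
|---|---|---|---|
| 3 times, all equal | 4.1% | 4.9% | 2.4–2.5% |
| 3 times, one clearly different | 4.8–5.0% | 4.8–5.0% | 1.5% |
| 4 times, all equal | 4.5–4.6% | 4.9–5.0% | 2.2–2.3% |
| 4 times, one differs by 0.5 SD | 7.6–8.7% | 9.2–10.2% | 1.6–1.8% |
| 4 times, one clearly different | 12.2–12.5% | 12.2–12.5% | 1.8–2.0% |
| 4 times, two equal pairs | 9.6–9.7% | 9.6–9.7% | 1.3–1.6% |

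**Holm, worst pattern.** The three pairs involving the shifted time are rejected first, so the three true-null pairs start at 0.05/3 = 0.0167, critical z = 2.394. P(range of three > 2.394 × √2 = 3.386) = 4.4%, within the stated alpha.

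**Power cost of Bonferroni over six.** The threshold is 0.05/6 = 0.0083, critical z = 2.638. A pair with 80% power at 0.05 has a standardised effect of 1.960 + 0.842 = 2.802. Its power becomes Φ(2.802 − 2.638) = Φ(0.164), about 56%.

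**The case against.** **The 12% is a maximum.** A reader might take it as the error rate for every variable. It is not: it needs one time to stand apart and the other three to be exactly equal. The error is about 5% or less when no time differs, and lies in between for intermediate patterns. This objection stands.

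**Four times is not secure for the metabolites.** If section 2.1 is right that blood was drawn three times, the gated procedure already holds about 5% for all seven metabolites, and the problem is confined to VAS. This also stands. It is why a reader should not multiply the 12% over seven metabolites and VAS to get a study-wide figure. That would need four times and the worst pattern for every variable, and any chance of at least one error would also need independence. Metabolites of one pathway measured in the same samples are unlikely to be independent.

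**Silence is not proof of unadjusted testing.** A reader might infer that the tests were certainly run without correction. The SAP does not say so, and it does call repeated measurements dependent groups, so the Bonferroni sentence could be stretched to cover them. Its position directly after the diagnostic-group tests makes that the less natural reading. What can be said is that no adjustment is stated.

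**These contrasts are secondary.** The Protocol's stated evaluation and the sample size concern the VAS-metabolite correlation. That is correct, and it limits the importance of the point without removing it.

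**Conclusion.** The point holds as a conditional one. No adjustment is stated for the pairwise Wilcoxon tests over time. Followed as written with four times, the procedure does not keep the per-variable family-wise error at the stated 0.05. The error can reach about 12% if one time clearly differs and the other three are equal, is roughly 8–10% in the intermediate patterns run, and is about 5% or less if no time differs. With three times it stays near 5%.

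This applies to VAS, provided that the recovery-unit record includes the VAS score, as both Protocol sections suggest. It applies to the metabolites only if section 2 rather than section 2.1 gives the right number of blood samples.

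The figures assume two-sided tests and normal data with equal within-patient correlation. Ties on the 0–10 VAS were not simulated. Nothing here touches the VAS-metabolite correlation.

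**What to change.** Add one sentence to the SAP: where a variable has four time points, pairwise Wilcoxon p-values after a significant overall test are Holm-adjusted within that variable over all six pairs, and adjusted p-values are reported. With three time points no adjustment is needed for error control, and the SAP can say so.

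Reconcile Protocol sections 2 and 2.1 on the number of blood samples, so that it is clear which rule each metabolite falls under.

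The cost is a rerun of existing output, with no new data, and some loss of power per pair. Holm is preferable to Bonferroni at 0.0083: it keeps the error within 5% and loses less power, and the fall from 80% to about 56% under Bonferroni is not slight.
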